15.1.2 Adverse device effect (ADE)

An adverse device effect is defined as an AE related to the use of an investigational medical device. This definition includes any adverse event resulting from insufficiencies or inadequacies in the instructions for use, the deployment, the implantation, the installation, the operation, or any malfunction of the investigational medical device as well as

any event that is a result of a use error or intentional misuse.

15.1.3 Serious adverse events (SAE)

Planned hospitalization for a pre-existing condition, or a procedure required by the clinical investigation plan, without serious deterioration in health, is not considered a serious adverse event.

A serious adverse event (SAE) or serious adverse reaction is defined as any adverse event/reaction that:

- Results in death
- Is life-threatening.
- Requires hospitalization or prolongation of current hospitalization.
- Results in persistent or significant disability or incapacity

Medical and scientific judgement will be exercised by the principal investigator in deciding whether an adverse event/reaction will be classified as serious.

15.1.4 Device deficiency (DD)

A device deficiency is defined as an inadequacy in the identity, quality, durability, reliability, safety, or performance of an investigational device. Device deficiencies include malfunctions, use errors, or inadequacy in information supplied by the manufacturer, including labelling.

15.1.5 Serious Adverse Device Effect (SADE)

A serious adverse device effect is an adverse device effect that has resulted in any of the consequences characteristic of a serious adverse event.

15.1.6 Unanticipated Serious Adverse Device Effect (USADE)

An unanticipated serious adverse device effect is a serious adverse device effect which by its nature, incidence, severity, or outcome has not been identified in the current risk assessment.

15.1.7 Significant Safety Issue (SSI)

SSI is defined by the NHMRC (2016) Guidance on safety monitoring and reporting in clinical trials involving therapeutic goods as:

A safety issue that could adversely affect the safety of participants or materially impact on the continued ethical acceptability or conduct of the trial.

15.1.8 Urgent Safety Measure (USM)

USM is defined by the NHMRC (2016) Guidance on safety monitoring and reporting in clinical trials involving therapeutic goods as:

A measure required to be taken to eliminate an immediate hazard to a participant's health or safety.

Note: This type of significant safety issue can be instigated by either the investigator or Sponsor and can be implemented before seeking approval from the Ethics Committee(s) or institutions.

15.2 Non-reportable adverse events

There are no non-reportable adverse events.

15.3 Causality

Each (serious) adverse event will be classified according to 4 different levels of causality:

- Unrelated
- Possibly
- Probably
- Definitively related

The Sponsor and the investigators will use the following definitions to assess the relationship of the (serious) adverse event to the investigational device or the investigation procedure.

Not related: relationship to the device, comparator or procedures can be excluded when:

- the event has no temporal relationship with the use of the investigational device or the procedures to application of the investigation device
- the (serious) adverse event does not follow a known response pattern to the medical device (if the response pattern is previously known) and is biologically implausible
- the discontinuation of medical device application or the reduction of the level of activation/exposure – when clinically feasible – and reintroduction of its use (or increase of the level of activation/exposure), do not impact on the serious adverse event
- the event involves a body-site or an organ that cannot be affected
- the (serious) adverse event can be attributed to another cause (e.g., an underlying or concurrent illness/ clinical condition, an effect of another device, drug, treatment, or other risk factors)
- harms to the participant are not clearly due to use error

Possibly: the relationship with the use of the investigational device or comparator, or the relationship with procedures, is weak but cannot be ruled out completely. Alternative causes are also possible (e.g., an underlying or concurrent illness/ clinical condition or/and an effect of another device, drug, or treatment). Cases where relatedness cannot be assessed, or no information has been obtained should also be classified as possible.

Probably: the relationship with the use of the investigational device or comparator, or the relationship with procedures, seems relevant and/or the event cannot reasonably be explained by another cause.

Definitely Related: the (serious) adverse event is associated with the investigational device, comparator, or with

procedures beyond reasonable doubt when:

- the event is a known side effect of the product category the device belongs to or of similar devices and procedures
- the event has a temporal relationship with investigational device use/application or procedures
- the event involves a body-site or organ that:
 - the investigational device or procedures are applied to
 - the investigational device or procedures have an effect on
- the event follows a known response pattern to the medical device (if the response pattern is previously known)
- the discontinuation of medical device application (or reduction of the level of activation/exposure) and reintroduction of its use (or increase of the level of activation/exposure), impact on the serious event (when clinically feasible)
- other possible causes (e.g., an underlying or concurrent illness/ clinical condition or/and an effect of another device, drug, or treatment) have been adequately ruled out
- harm to the participant is due to error in use
- the event depends on a false result given by the investigational device used for diagnosis, when applicable

In order to establish the relatedness, not all the criteria listed above might be met at the same time, depending on the type of device/procedures and the serious event.

The Sponsor and the investigators will distinguish between the (serious) adverse events related to the investigational device and those related to the procedures (any procedure specific to the clinical investigation). An adverse event can be related both to procedure and the investigational device. Complications caused by concomitant treatments not imposed by the clinical investigation plan are considered not related. Similarly, several routine diagnostic or patient management procedures are applied to patients regardless of the clinical investigation plan. If routine procedures are not imposed by the clinical investigation plan, complications caused by them are also considered not related.

In some particular cases the event may be not adequately assessed because information is insufficient or contradictory and/or the data cannot be verified or supplemented. The Sponsor and the investigators will make the maximum effort to define and categorize the event and avoid these situations. Where an investigator assessment is not available and/or the Sponsor remains uncertain about classifying the (serious) adverse event, the sponsor should not exclude the relatedness; the event should be classified as “possible” and the reporting not be delayed.

Particular attention shall be given to the causality evaluation of unanticipated serious adverse events. The occurrence of unanticipated events related to the use of the device could suggest that the clinical investigation places subjects at increased risk of harm than was to be expected beforehand.

15.4 Severity

Each (serious) adverse event will be classified according to three (3) levels of severity. The Sponsor and the

investigators will use the following definitions to assess the severity of the (serious) adverse event:

Mild: Awareness of signs or symptoms, but easily tolerated and are of minor irritant type causing no loss of time from normal activities. Symptoms do not require therapy or a medical evaluation; signs and symptoms are transient.

Moderate: Events introduce a low level of inconvenience or concern to the participant and may interfere with daily activities, but are usually improved by simple therapeutic measures; moderate experiences may cause some interference with functioning.

Severe: Events interrupt the participant's normal daily activities and generally require systemic drug therapy or other treatment; they are usually incapacitating

15.5 Reporting Requirements

15.5.1 Reporting (Serious) Adverse Events

Adverse event reporting will start at the time of signing consent. Underlying diseases are not reported as adverse events, but any deterioration in severity will be reported.

Adverse event information will be collected for all participants. At every participant visit, the investigator will determine whether an adverse event has occurred since the last visit. All adverse events will be reported in the CRF. The date of the initial event and the subsequent treatment will be documented.

The Investigator will be required to report any and all Serious Adverse Events (SAEs) that occur throughout the course of the study, regardless of causality or expectedness, to the Sponsor or designee within 24 hours of knowledge of the event.

Minimum information on the case report form will include:

- Participant initials and study number
- Nature of the event
- Commencement and cessation of the event
- An investigator's opinion of the relationship between study involvement and the event (unrelated, possibly, probably or definitively related).
- Whether treatment was required for the event and what treatment was administered.

The Sponsor is responsible to assess whether the SAE meets requirements for expedited reporting.

15.5.2 Reporting Device Deficiencies

All device deficiencies related to the identity, quality, durability, reliability, safety, or performance of an investigational

medical device shall be documented throughout the clinical investigation and appropriately managed by the Sponsor. For device deficiencies the investigator will describe any action other than any corrective or remedial actions taken to prevent recurrence of the deficiency. A remedial action is any action other than routine maintenance or servicing of a medical device where such action is necessary to prevent recurrence of a device deficiency. This includes any amendment to the device design to prevent recurrence.

15.6 Expedited Reporting

15.6.1 Unexpected Serious Adverse Device Effects (USADEs)

The Sponsor is responsible for assessing safety information received from Investigators and must reporting all fatal or life threatening USADEs to the HREC and the TGA no later than 7 calendar days after being made aware of the case. Any follow-up information must be supplied within a further 8 calendar days.

For all other USADEs that are not fatal or life-threatening, the HREC and the TGA must be notified by the Sponsor no later than 15 calendar days after being made aware of the case.

15.6.2 Significant Safety Issues (SSI)

The Sponsor must notify the TGA, the HREC and Investigators of all significant safety issues (SSI) that adversely affect the safety of participants or materially impact on the continued ethical acceptability or conduct of the trial within 15 calendar days of the Sponsor being made aware of the issue.

15.6.3 Urgent Safety Measure (USM)

The Sponsor must notify the TGA, the HREC and Investigators of all significant safety issues (SSI) that meet the definition of an urgent safety measure (USM) as soon as possible but must be within 72 hours.

15.7 Emergency Contacts:

Emergency contact details for the reporting of SAEs, device deficiencies, SAEs and USADEs are as follows:

| | Sponsor | Avania Pty Ltd |
|----------|----------------------------|-------------------------------|
| Name | [name] | [name] |
| Position | Clinical Trial Coordinator | Project Manager |
| Email | [contact] | [contact] |
| Phone | [contact] | [contact] [name] |

15.8 Safety Data Monitoring Committee

An independent Safety Data Monitoring Committee (SDMC) will be established to assess study outcome and safety

data at periodic points during study enrolment and recommend if the study should be continued, revised or closed. These reviews will provide assurance that the product is safe for use and will support continued investigation of the JSI. The SDMC will be comprised of group of independent medical clinicians and a biostatistician. SDMC members will not have any conflicts of interest which may affect objectivity. The SDMC's activities and responsibilities will be governed by the SDMC Charter.

After the first 5 participants are treated through the operating room, the SDMC will review the data for efficacy, reliability and safety outcomes prior to enrolling further participants.

15.9 Prior or Concomitant Medications

Administration of concomitant medications before, during and after the stent insertion shall be consistent with standard of care, usual practice, international guidelines and general recommendations, according to the participants' medical condition. All medications, including OTC medications, vitamins, and herbal supplements, and non-drug therapies taken or administered by participants during the study will be recorded in the eCRF.

16 AMENDMENTS, DEVIATIONS AND WAIVERS

16.1 Amendments

Investigators may not modify (amend) this clinical investigation plan without obtaining written concurrence of the Sponsor, involved Ethics Committee(s), and applicable regulatory authorities.

16.2 Deviations and Waivers

Investigators may not deviate from this clinical investigation plan without first receiving approval in writing from the Sponsor, involved Ethics Committee(s), and applicable regulatory authorities, except to protect the rights, safety and well-being of human subjects under emergency circumstances. All deviations will be documented on eCRFs.

The use of waivers from the Clinical Investigation Plan is prohibited.

16.2.1 Reporting

Investigators will also adhere to procedures for reporting deviations to the involved Ethics Committee(s) in accordance with their specific reporting policies and procedures.

Under emergency circumstances, deviations from the clinical investigation plan to protect the rights, safety and wellbeing of human subjects may proceed without prior approval of the sponsor and the Ethics Committee(s). Such deviations shall be documented and reported to the sponsor and the Ethics Committee(s) as soon as possible, but no later than 24 hours after the investigator had been made aware.

Deviations from the clinical investigation plan to the inclusion or exclusion criteria and deviations that affect the primary endpoints are considered major deviations. Deviations that may affect the secondary endpoints are considered minor deviations. All deviations will be reviewed by the medical monitor. The medical monitor is

responsible for major/minor classification of the deviations.

16.2.2 Corrective and preventive actions *code*

JiffyStent Pty Ltd or its representatives will evaluate deviations to the clinical investigation plan during monitoring visits. Individual event corrective and preventive actions may be recommended at that time. In addition, deviations occurring across investigational sites will be reviewed by JiffyStent Pty Ltd on a periodic basis to determine if more global preventive actions may be required.

16.2.3 Investigator disqualification criteria

JiffyStent Pty Ltd reserves the right to terminate an investigator/investigational site for any of the following reasons:

- Failure to secure subject informed consent including protection of personal data prior to enrolment.
- Failure to report safety events within 24 hours of discovery after learning of the event.
- Failure to report serious adverse device effects within 24 hours of discovery.
- Repeated investigational plan deviations.
- Repeated failure to appropriately complete case report forms.
- Failure to enrol an adequate number of subjects. Loss of or unaccounted for investigational product inventory

16.2.4 Follow-up management

Section 9 describes the procedures and precautions taken for participants following the end or early termination of the investigation or for participants who are lost to follow-up or withdraw their consent. Participants will receive standard of care in case a protocol deviation leads to the end, temporary halt, or early termination of the investigation. The standard of care is defined by the applicable treatment protocol(s) at the investigational site.

Any unresolved (S)AEs at a participants' final study visit must be marked unresolved on the eCRF AE form. Any (S)AE that is related to the study device and unresolved at the end of the study will be followed by the investigator until resolution or for 30 days after the last study visit if the treatment plan can be transferred to the primary physician or specialist or is determined to be irreversible.

Participants withdrawn due to an adverse event will be followed for 30 days or until resolution of the adverse event, whichever is the shorter time. After study end, participants will receive medical care according to standard of care.

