8.3 STUDY OUTCOME MEASURES

8.3.1 Primary endpoint:

- The ability of the JSI to correctly insert a stent into the ureter of a suitable participant as determined by post-stenting KUB plain X-ray.
 - Timepoint: Immediately post-stent insertion with KUB Xray
 - Measure: Investigator's assessment of position of superior part of stent within kidney collecting system on KUB plain X-ray performed after stent insertion (Yes/No/Unsure)
 - If "Unsure"- proceed to renal ultrasound to confirm.
 - If "No" or still "Unsure" then proceed to standard stent insertion in operating room

8.3.2 Secondary endpoints:

- The mechanical reliability of the JSI to perform its function correctly as determined by the treating doctor as noted on a global doctor satisfaction score.
 - Timepoint: Immediately post-device usage
 - Measure: Rating of device reliability, i.e. correct mechanical function to work as intended on global doctor satisfaction score.
- The clinical safety of the JSI.
 - Timepoint: Immediately post-intervention commencement through to final follow up visit.
 - Measure: Assessed using reported adverse events, device deficiencies and participant questionnaire.
- Time taken to insert the ureteric stent using JSI (measures stent insertion procedure time only, workflow data assesses overall workflow and will be assessed separately).
 - Timepoint: Immediately post-intervention commencement.
 - Measure: Use of stopwatch or calculated from start and end times and recorded on a

case report form.

- Feasibility- evaluation of participant recruitment rate.
 - Timepoint- At study completion. To be completed within 6 months of study commencement.
 - Measure: A log will be kept of all participants invited to the study and if applicable, their reasons for refusal noted. Feasibility will be assessed using recruitment/withdrawal data and an audit of study enrolment and withdrawal logs.
- Participant experience and satisfaction with the JSI.
 - Timepoint: Prior to stent insertion (within 2 hours), Post stent insertion (within 1 hour), and at follow up visit for definitive stone management surgery (within 14-21 days)
 - Measure: Participants will receive a Patient Satisfaction Questionnaire regarding their experience of ureteric stent insertion with the JiffyStent Inserter.
- User satisfaction for urological doctor/study researcher.
 - Timepoint- Immediately after stent-insertion.

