9.8 End of treatment

The end of treatment is defined as the day the decision was made to permanently discontinue all study treatment and participant engagement. End of treatment is the date of final participant survey completion and definitive stone

management surgery (14-21 days post enrolment). Each participant will be followed through to the end of treatment, unless he/she has died or withdrawn consent, or the study is terminated.

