12 PARTICIPANT DISCONTINUATION/WITHDRAWAL

A participant will be discontinued from the study for any of the following reasons:

- Withdrawal of consent
- Lost to follow-up (LTFU)

When a participant withdraws before study completion, the reason for withdrawal is to be documented in both the

eCRF and in the source document. If the reason for withdrawal from the study is withdrawal of consent, then no additional study assessments are allowed. In the situation where a study participant has an indwelling ureteric stent, arrangements will be made for the participants to return to the study site for definitive stone management and stent removal.

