12.1 Withdrawal of consent

A participant may withdraw from the study at any time at his/her or own request or may be withdrawn at any time at the discretion of the investigator for safety behavioural compliance or administrative reasons. This is expected to be uncommon.

If a participant notifies an investigator that he/she would like to withdraw consent from the study, the investigator should discuss any potential medical risks of withdrawal and must schedule definitive stone management surgery and stent removal (if required), and ongoing medical evaluation/follow up at site.

If the participant withdraws consent for disclosure of future information, the sponsor may retain and continue to use any data collected before such a withdrawal of consent.

When a participant withdraws before study completion the reason for withdrawal is to be documented in the eCRF and in the source document. If the reason for withdrawal from the study is withdrawal of consent, then no additional assessments are allowed. If a participant withdraws the subject can be replaced to achieve targeted enrolment numbers.

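### Section 16.2.4 lets study safety follow-up of a participant withdrawn for an adverse event stop when the event resolves, possibly before the Day 14-21 visit, contrary to 9.8 and the safety window in 8.3.2

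*Protocol*

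**What the plan says.** Section 16.2.4 sets the rule for this group: participants "withdrawn due to an adverse event will be followed for 30 days or until resolution of the adverse event, whichever is the shorter time". It applies to any adverse event that leads to withdrawal, device-related or not. The paragraph just before it treats device-related events still open at study end differently. They are followed until they resolve, and a limit of 30 days after the last visit applies only if care can be handed over or the event is judged irreversible.

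Section 9.8 gives the general rule: "Each participant will be followed through to the end of treatment, unless he/she has died or withdrawn consent, or the study is terminated". It defines the end of treatment twice. One sentence reads "The end of treatment is defined as the day the decision was made to permanently discontinue all study treatment and participant engagement". The next ties it to events: "End of treatment is the date of final participant survey completion and definitive stone" surgery, at 14-21 days.

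Section 8.3.2 sets the time window of the clinical safety endpoint as "Immediately post-intervention commencement through to final follow up visit". Its measures are adverse events, device deficiencies and the participant questionnaire. Sections 9.2 and 9.9 place that visit 14 to 21 days after stent insertion.

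On the route to withdrawal, section 12 opens with "A participant will be discontinued from the study for any of the following reasons" and lists only withdrawn consent and loss to follow-up. Section 12.1, under a heading about consent, adds that a participant "may be withdrawn at any time at the discretion of the investigator for safety behavioural compliance or administrative reasons".

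**The concern.** One inserter is used once per participant and then removed (6.9, 6.10). Withdrawal after that point stops no exposure to the inserter; it stops observation. The stent stays in until definitive stone surgery, and section 11.2.1 expects events in that interval: blood in the urine, urinary infection, and migration of a stent that was first placed correctly.

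A site that follows 16.2.4 literally may therefore stop collecting safety data as soon as the triggering event settles, although 8.3.2 defines the safety endpoint up to the final visit. This is a first-in-human study in which safety is a main objective. Adverse-event data that the protocol allowed a site not to collect cannot be recovered at the analysis stage.

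**Working it through.** The protocol gives no figure to reproduce. The check compares passages and counts days.

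**Passages side by side**

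| Source | Follow-up ends at | Is withdrawal for an adverse event an exception? |
|---|---|---|
| 9.8 | Final survey and stone surgery, 14-21 days | No; only death, withdrawn consent, study termination |
| 8.3.2, safety | Final follow-up visit | No exception stated |
| 16.2.4, device-related events open at study end | Resolution; 30 days after last visit only under conditions | Not addressed |
| 16.2.4, withdrawn for an adverse event | Shorter of resolution and 30 days | This is the rule for that group |
| 12 and 12.1 | Return for stone management and stent removal | Clinical care; study adverse-event collection is not restored |

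**Day count.** Take insertion as day 0, withdrawal on day *w*, resolution on day *r* (with *r* no earlier than *w*), and the visit on day *V*, between 14 and 21 as in 9.9. Follow-up under 16.2.4 ends on day min(*r*, *w* + 30). The unobserved time is *V* minus that day, when positive.

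*Resolution limb.* The values of *r* are illustrative; the protocol gives none.
- *r* = 3: 14 − 3 = 11 to 21 − 3 = 18 days.
- *r* = 7: 14 − 7 = 7 to 21 − 7 = 14 days.
- *r* = 10: 14 − 10 = 4 to 21 − 10 = 11 days.

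*30-day limb.* The earliest it can act after insertion is *w* = 0, giving day 30. That is 30 − 21 = 9 to 30 − 14 = 16 days after the visit. It cuts the window short only if surgery slips beyond 30 days after withdrawal. The synopsis says only that surgery usually falls within 14-21 days, so this is possible but not the planned course.

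The truncation therefore comes from the resolution limb combined with the choice of the shorter period.

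**Share of the sample.** Section 9.1 plans 5 participants in Group 1 and 5-10 in Group 2, so 10-15 in all. One participant with a cut-off window is 1/15 = 6.7% to 1/10 = 10% of the total, or 1/10 = 10% to 1/5 = 20% of Group 2.

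**The case against.** The best defence on the text is the first definition in 9.8. If treatment ends on the day of the decision to discontinue, a participant withdrawn for an adverse event has been followed to that point and 9.8 is satisfied. But the next sentence of 9.8 names the final survey and surgery, and on the first definition the exception for withdrawn consent would have no work to do. The window in 8.3.2 conflicts with 16.2.4 on either reading.

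A second defence is that much is covered elsewhere. Section 15.5.1 collects adverse events for all participants and requires serious ones to be reported throughout the study. The bar on further assessments in sections 12 and 12.1 applies only to withdrawn consent. This narrows the gap mainly to non-serious events and the final questionnaire. It does not close it, because 15.5.1 asks about events at participant visits and 16.2.4 is the specific rule for those withdrawn.

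Third, the case should be rare: 12.1 expects withdrawal to be uncommon. The rule also has an ordinary use before the device is used, since adverse-event reporting starts at consent. Both points stand and limit the expected frequency.

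Several stronger readings are tempting, and the protocol does not support them:
- *Those who fare worst are watched least.* Early exit needs the event to have resolved. A persisting event is followed for up to 30 days, past a visit at 14-21 days.
- *The loss falls on those harmed by the device.* The rule covers any adverse event; device harm is a subset.
- *A device-related event open at 30 days is simply dropped.* The preceding paragraph of 16.2.4 is not expressly limited to participants still in the study. The two sentences are unclear together, but they do not plainly drop the event.
- *The stent is abandoned.* Section 12 arranges the return for stone management and stent removal.
- *Ureteric stricture would be missed because of this rule.* Section 11.2.1 describes it as long-term, so a visit at 14-21 days might not capture it either.
- *The participant leaves the safety denominator.* Section 14.8 keeps partial data from those who drop out.

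**Conclusion.** The inconsistency is real and limited. Followed as written, 16.2.4 allows study safety follow-up to end before the final visit, against 9.8 and 8.3.2, and its two paragraphs do not give one rule for unresolved device-related events. The data at risk are adverse events between resolution and the visit, mainly non-serious ones, and the final questionnaire. The primary endpoint, read straight after insertion, is not affected.

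Each affected participant is at least 6.7% of the sample. This is the share with an incomplete safety window, not a share removed from the denominator. The days lost depend on when the event resolves, which the protocol cannot tell us. The conclusion assumes withdrawal after device use, resolution before the visit, and a visit counted from insertion as in 9.9; 9.8 counts from enrolment instead.

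**What to change.** Reconcile 16.2.4, 9.8, 8.3.2, 12 and 12.1 on the collection of safety data:

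- In 16.2.4, delete the clause that selects the shorter period. Deletion alone would leave two alternatives with no rule for choosing, so add that, unless consent is withdrawn, adverse-event collection after use of the inserter continues at least through the Day 14-21 visit and stent removal. It can be done at the visit or by the medical-record review already provided for in 9.9.
- State that unresolved device-related events follow the same rule whether or not the participant was withdrawn.
- Say whether the final questionnaire is still collected from these participants.
- In 9.8, keep one definition of end of treatment.
- Leave the investigator's discretion to withdraw in 12.1 unchanged, but bring it into line with the list of reasons in section 12.

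These are wording changes about data collection. They alter no treatment and add no visit, because these participants are to return for stone management and stent removal anyway. The cost is slightly more data entry.
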